8.3.2 Placebo for p24CE1/2 + *IL-12* pDNA (Group 1)

One vial containing Sodium Chloride for Injection, USP 0.9% will be needed to prepare the two syringes. The vial should be visually inspected prior to use. The pharmacist will also inspect the sterile pouches containing the TriGridTM Application Cartridges for integrity and verify the Cartridges have not passed expiration. If any tears or gaps in the sterile pouch are noted or if the expiration date has been reached, the Application Cartridge should be placed in quarantine and the protocol pharmacist should be informed. Note: In the event that the Cartridge Cap has become detached from the Cartridge in the sterile pouch, the Cartridge may still be used if the Cartridge Cap can be replaced without contaminating the patient contact portion of the Cartridge.

• Using aseptic technique, the pharmacist, using two new 3 mL syringes (BD# 309585, 309657, or Ichor approved) each fitted with a 22 Ga x 1.5" needle (BD# 305156 or Ichor approved), will withdraw 1 mL of the Sodium Chloride for Injection, USP 0.9% into each syringe and insert the syringe with an identical new needle attached into the Application Cartridge as directed in the *HVTN 119 Study Specific Procedures*.

Note: Use the syringe tabs to insert the syringe into the Application Cartridge. Do not depress the syringe plunger during insertion of the syringe into the Application Cartridge as this will cause the agent to be injected into the Cartridge.

Caution: During the syringe loading procedure, do not physically touch the syringe needle or cause it to come in contact with a non-sterile surface. Note that, although the inside of the Application Cartridge is sterile, contact between the syringe needle and the inner housing of the Application Cartridge should be avoided to the extent possible. Contact between the syringe needle and Application Cartridge could result in deformation of the syringe needle and increased discomfort for the subject upon insertion. If contamination and/or deformation of the injection needle is suspected, replace the injection needle with a new BD 22 Ga x 1.5" injection needle (BD model 305156 or Ichor approved). To prevent loss of dosage make sure to withdraw agent from needle before replacing.

- Each Application Cartridge will have the Participant's ID number written on it using a Sharpie or other similar pen. The cartridge will then be placed back in the pouch that it was removed from and the pouch will be labeled as "HVTN 119 study product or placebo 1mL."
- The pouch containing the syringe must be labeled with a four-hour expiration date from the time the vial is removed from the refrigerator. The label must also contain the words "Administer as soon as possible."
- One of the syringes must also be labeled for administration in RIGHT deltoid and the second syringe must be labeled for administration in the LEFT deltoid.

Any unused portion of reconstituted vials or expired prefilled syringes is disposed of in accordance with institutional or pharmacy policy.

8.3.3 p24CE1/2 + p55^{gag} + /L-12 pDNA (Group 1)

One vial of p24CE1/2 pDNA (4 mg/mL), 1 vial of p55^{gag} pDNA (4 mg/mL), 2 vials of *IL-12* pDNA (2 mg/mL) and one empty 5 mL sterile vial (for mixing) will be needed to prepare the dose. Prior to dispensing, the pharmacist will remove one vial of p24CE1/2 pDNA and one vial of $p55^{gag}$ pDNA from the freezer and allow to thaw at room temperature for 15 to 30 minutes until no crystals are observed. The pharmacist will remove 2 vials of *IL-12* pDNA from the refrigerator. Gently swirl and invert the vials containing vaccine for at least 10 inversions (do not shake vigorously).

The vials should be visually inspected prior to use. If the vial contains material different from its description above, do not use the vial and contact the protocol pharmacist. Prior to mixing the study products, the pharmacist will also inspect the sterile pouches containing the TriGridTM Application Cartridges for integrity and verify the Cartridges have not passed expiration. If any tears or gaps in the sterile pouch are noted or if the expiration date has been reached, the Application Cartridge should be placed in quarantine and the protocol pharmacist should be informed. *Note: In the event that the Cartridge Cap has become detached from the Cartridge in the sterile pouch, the Cartridge may still be used if the Cartridge Cap can be replaced without contaminating the patient contact portion of the Cartridge.*

- Using aseptic technique, the pharmacist will withdraw 0.6 ml from the vial containing p24CE1/2 pDNA (4 mg/mL) with a 1 mL low void 25 Ga syringe (low dead space syringe; see *HVTN 119 Study Specific Procedures*) and inject this into the mixing vial. This mixing vial, now containing 0.6 mL of p24CE1/2 pDNA, will be set aside.
- Using aseptic technique, the pharmacist will withdraw 0.6 ml from the vial containing p55^{gag} pDNA (4 mg/mL) with a 1 mL low void 25 Ga syringe (low dead space syringe; see *HVTN 119 Study Specific Procedures*) and inject this into the mixing vial that contains p24CE1/2 pDNA. This mixing vial, now containing 1.2 mL of p24CE1/2 pDNA + p55^{gag} pDNA will be set aside.
- Using aseptic technique, the pharmacist will then withdraw 0.6 mL from each of the 2 vials containing *IL-12* pDNA (2 mg/mL) with a 1 mL syringe and inject them directly into the mixing vial containing 1.2 mL of p24CE1/2 pDNA+ p55^{gag}pDNA. The pharmacist will mix the vial containing 2.4 mL of the mixture of p24CE1/2 pDNA + p55^{gag} pDNA + GENEVAX® IL-12 DNA plasmid. Gently swirl and invert the mixing vial containing the vaccine mixture for at least 10 inversions (do not shake vigorously).
- Using two new 3 mL syringes (BD# 309585, 309657, or Ichor approved) each fitted with a 22 Ga x 1.5" needle (BD# 305156 or Ichor approved), the pharmacist will withdraw 1 mL of the mixed preparation from the mixing vial into each syringe, and insert each syringe with an identical new needle attached into an Application Cartridge as directed in the *HVTN 119 Study Specific Procedures*.

Note: Use the syringe tabs to insert the syringe into the Application Cartridge. Do not depress the syringe plunger during insertion of the syringe into the Application Cartridge as this will cause the agent to be injected into the Cartridge.

Caution: During the syringe loading procedure, do not physically touch the syringe needle or cause it to come in contact with a non-sterile surface. Note that, although the inside of the Application Cartridge is sterile, contact between the syringe needle and the inner housing of the Application Cartridge should be avoided to the extent possible. Contact between the syringe needle and Application Cartridge could result in deformation of the syringe needle and increased discomfort for the subject upon insertion. If contamination and/or deformation of the injection needle is suspected, replace the injection needle with a new BD 22 Ga x 1.5" injection needle (BD model 305156 or Ichor approved). To prevent loss of dosage make sure to withdraw agent from needle before replacing.

- Each Application Cartridge will have the Participant's ID number written on it using a Sharpie or other similar pen. The cartridge will then be placed back in the pouch that it was removed from and the pouch will be labeled as "HVTN 119 study product or placebo 1mL."
- The pouch containing the syringe must be labeled with a four-hour expiration date from the time the vial is removed from the refrigerator. The label must also contain the words "Administer as soon as possible."
- One of the syringes must also be labeled for administration in RIGHT deltoid and the second syringe must be labeled for administration in the LEFT deltoid.

Any unused portion of reconstituted vials or expired prefilled syringes is disposed of in accordance with institutional or pharmacy policy.

8.3.4 Placebo for p24CE1/2+ p55^{gag} + *IL-12* pDNA (Group 1)

One vial containing Sodium Chloride for Injection, USP 0.9% will be needed to prepare the two syringes. The vial should be visually inspected prior to use. The pharmacist will also inspect the sterile pouch containing the TriGridTM Application Cartridge for integrity and verify the Cartridge has not passed expiration. If any tears or gaps in the sterile pouch are noted or if the expiration date has been reached, the Application Cartridge should be placed in quarantine and the protocol pharmacist should be informed. *Note: In the event that the Cartridge Cap has become detached from the Cartridge in the sterile pouch, the Cartridge may still be used if the Cartridge Cap can be replaced without contaminating the patient contact portion of the Cartridge.*

• Using aseptic technique, the pharmacist, using two new 3 mL syringes (BD# 309585, 309657, or Ichor approved) each fitted with a 22 Ga x 1.5" needle (BD# 305156 or Ichor approved), will withdraw 1 mL of the Sodium Chloride for Injection, USP 0.9% into each syringe and insert the syringe with an identical new needle attached into the Application Cartridge as directed in the *HVTN 119 Study Specific Procedures*.

Note: Use the syringe tabs to insert the syringe into the Application Cartridge. Do not depress the syringe plunger during insertion of the syringe into the Application Cartridge as this will cause the agent to be injected into the Cartridge.

Caution: During the syringe loading procedure, do not physically touch the syringe needle or cause it to come in contact with a non-sterile surface. Note that, although the inside of the Application Cartridge is sterile, contact between the syringe needle and the inner housing of the Application Cartridge should be avoided to the extent possible. Contact between the syringe needle and Application Cartridge could result in deformation of the syringe needle and increased discomfort for the subject upon insertion. If contamination and/or deformation of the injection needle is suspected, replace the injection needle with a new BD 22 Ga x 1.5" injection needle (BD model 305156 or Ichor approved). To prevent loss of dosage make sure to withdraw agent from needle before replacing.

• Each Application Cartridge will have the Participant's ID number written on it using a Sharpie or other similar pen. The cartridge will then be placed back in the

pouch that it was removed from and the pouch will be labeled as "HVTN 119 study product or placebo 1 mL."

- The pouch containing the syringe must be labeled with a 4-hour expiration date from the time the vial is removed from the refrigerator/freezer. The label must also contain the words "Administer as soon as possible."
- One of the syringes must also be labeled for administration in RIGHT deltoid and the second syringe must be labeled for administration in the LEFT deltoid.

Any unused portion of reconstituted vials or expired prefilled syringes is disposed of in accordance with institutional or pharmacy policy.

Any unused portion of entered vials or expired prefilled syringes should be disposed of in accordance with institutional or pharmacy policy.

8.3.5 **p55**^{*gag*} + *IL*-12 **pDNA (Group 2)**

Two vials of $p55^{gag}$ pDNA (4 mg/mL), 2 vials of *IL-12* pDNA (2 mg/mL), and 1 empty sterile vial (5 mL) will be needed to prepare the 2 syringes. Prior to dispensing, the pharmacist will remove 2 vials of $p55^{gag}$ pDNA from the freezer and allow thaw at room temperature for 15-30 minutes until no crystals are observed. The pharmacist will remove 2 vials of *IL-12* pDNA from the refrigerator. Gently swirl and invert the vials for at least 10 inversions (do not shake vigorously).

The vials should be visually inspected prior to use. If the vial contains material different from its description above, do not use the vial and contact the protocol pharmacist. Prior to mixing the study products, the pharmacist will also inspect the sterile pouches containing the TriGridTM Application Cartridges for integrity and verify the Cartridges have not passed expiration. If any tears or gaps in the sterile pouch are noted or if the expiration date has been reached, the Application Cartridge should be placed in quarantine and the protocol pharmacist should be informed. *Note: In the event that the Cartridge Cap has become detached from the Cartridge in the sterile pouch, the Cartridge may still be used if the Cartridge Cap can be replaced without contaminating the patient contact portion of the Cartridge.*

- Using aseptic technique, the pharmacist will withdraw 0.6 mL from each of the 2 vials of p55^{gag} pDNA (4 mg/mL) with a 1 mL low void 25 Ga syringe (low dead space syringe; see *HVTN 119 Study Specific Procedures*) and inject this into the mixing vial. This mixing vial, now containing 1.2 mL of p55^{gag}pDNA, will be set aside.
- Using aseptic technique, the pharmacist will then withdraw 0.6 mL from each of the 2 vials containing *IL-12* pDNA (2 mg/mL) with a 1 mL syringe and inject them directly into the mixing vial containing 1.2 mL of p55^{gag} pDNA. Now the mixing vial contains 2.4 mL of the mixture of p55^{gag} pDNA + GENEVAX® IL-12 DNA plasmid. The pharmacist will gently swirl and invert the mixing vial containing the vaccine mixture for at least 10 inversions (do not shake vigorously).
- Using two new 3 mL syringes (BD# 309585, 309657, or Ichor approved) each fitted with a 22 Ga x 1.5" needle (BD# 305156, or Ichor approved), the

pharmacist will withdraw 1 mL of the mixed preparation from the mixing vial into each syringe, and insert each syringe with an identical new needle attached into an Application Cartridge as directed in the *HVTN 119 Study Specific Procedures*.

Note: Use the syringe tabs to insert the syringe into the Application Cartridge. Do not depress the syringe plunger during insertion of the syringe into the Application Cartridge as this will cause the agent to be injected into the Cartridge.

Caution: During the syringe loading procedure, do not physically touch the syringe needle or cause it to come in contact with a non-sterile surface. Note that, although the inside of the Application Cartridge is sterile, contact between the syringe needle and the inner housing of the Application Cartridge should be avoided to the extent possible. Contact between the syringe needle and Application Cartridge could result in deformation of the syringe needle and increased discomfort for the subject upon insertion. If contamination and/or deformation of the injection needle is suspected, replace the injection needle with a new BD 22 Ga x 1.5" injection needle (BD model 305156 or Ichor approved). To prevent loss of dosage make sure to withdraw agent from needle before replacing.

- Each Application Cartridge will have the Participant's ID number written on it using a Sharpie or other similar pen. The cartridge will then be placed back in the pouch that it was removed from and the pouch will be labeled as "HVTN 119 or placebo 1 mL."
- The pouch containing the syringe must be labeled with a 4-hour expiration date from the time the vial is removed from the refrigerator/freezer. The label must also contain the words "Administer as soon as possible."
- One of the syringes must also be labeled for administration in RIGHT deltoid and the second syringe must be labeled for administration in the LEFT deltoid.

Any unused portion of reconstituted vials or expired prefilled syringes is disposed of in accordance with institutional or pharmacy policy.

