6.3 Blinding

Participants and site staff (except for site pharmacists) will be blinded as to participant treatment arm assignments (ie, blinded to both group and vaccine/control status). Study product assignments are accessible to those HVTN CRS pharmacists, DAIDS protocol

pharmacists and contract monitors, and SDMC staff who are required to know this information in order to ensure proper trial conduct. Any discussion of study product assignment between pharmacy staff and any other HVTN CRS staff is prohibited. The HVTN SMB members also are unblinded to treatment assignment in order to conduct review of trial safety.

When a participant leaves the trial prior to study completion, the participant will be told he or she must wait until all participants are unblinded to learn his or her treatment assignment.

Emergency unblinding decisions will be made by the site investigator. If time permits, the HVTN PSRT should be consulted before emergency unblinding occurs.

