6.4.3.1 Reactogenicity

The number and percentage of participants experiencing each type of reactogenicity sign or symptom will be tabulated by severity and treatment arm and the percentages displayed graphically by arm. For a given sign or symptom, each participant's reactogenicity will be counted once under the maximum severity for all injection visits. In addition, to the individual types of events, the maximum severity of local pain or tenderness, induration or erythema, and of systemic symptoms will be calculated. Kruskal-Wallis tests will be used to test for differences in severity between arms.

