8.1 Vaccine regimen

The schedule of vaccination is shown in Section 3 and additional information is given below.

Group 1

All vaccine regimens including placebo will be administered intramuscularly using the Ichor Medical System intramuscular TriGrid TM Delivery System (TDS-IM) electroporation (EP) device.

Treatment 1 (T1):

p24CE1/2 DNA plasmid 2 mg admixed with GENEVAX[®] IL-12 DNA plasmid 1 mg administered as 1 mL IM in left deltoid

AND

p24CE1/2 DNA plasmid 2 mg admixed with GENEVAX[®] IL-12 DNA plasmid 1 mg administered as 1 mL IM in right deltoid at Months 0 and 1.

THEN

p24CE1/2 DNA plasmid 1 mg admixed with p55 gag DNA plasmid 1 mg and GENEVAX® IL-12 DNA plasmid 1 mg administered as 1 mL IM in left deltoid

AND

p24CE1/2 DNA plasmid 1 mg admixed with p55^{gag} DNA plasmid 1 mg and GENEVAX® IL-12 DNA plasmid 1 mg administered as 1 mL IM in right deltoid at Months 3 and 6.

Control 1 (C1):

Placebo for p24CE1/2 + *IL-12* pDNA is Sodium Chloride for Injection, USP 0.9%, administered as 1 mL IM in left deltoid

AND

1 mL IM in right deltoid at Months 0 and 1.

THEN

Placebo for $p24CE1/2 + p55^{gag} + IL-12$ pDNA is Sodium Chloride for Injection, USP 0.9%, administered as 1 mL IM in left deltoid

AND

1 mL IM in right deltoid at Months 3 and 6.

Group 2

All vaccine regimens including placebo will be administered intramuscularly using the Ichor Medical System intramuscular TriGrid TM Delivery System (TDS-IM) electroporation (EP) device.

Treatment 2 (T2):

p55^{gag} DNA plasmid 2 mg admixed with GENEVAX[®] IL-12 DNA plasmid 1 mg administered as 1 mL IM in left deltoid

AND

p55^{gag} DNA plasmid 2 mg admixed with GENEVAX[®] IL-12 DNA plasmid 1 mg administered as 1 mL IM in right deltoid at Months 0, 1, 3, and 6.

Control 2 (C2):

Placebo for $p55^{gag} + IL-12$ pDNA is Sodium Chloride for Injection, USP 0.9%, administered as 1 mL IM in left deltoid

AND

1 mL IM in right deltoid at Months 0, 1, 3 and 6.

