Caution: During the syringe loading procedure, do not physically touch the syringe needle or cause it to come in contact with a non-sterile surface. Note that, although the inside of the Application Cartridge is sterile, contact between the syringe needle and the inner housing of the Application Cartridge should be avoided to the extent possible. Contact between the syringe needle and Application Cartridge could result in deformation of the syringe needle and increased discomfort for the subject upon insertion. If contamination and/or deformation of the injection needle is suspected, replace the injection needle with a new BD 22 Ga x 1.5" injection needle (BD model 305156 or Ichor approved). To prevent loss of dosage make sure to withdraw agent from needle before replacing.

- Each Application Cartridge will have the Participant's ID number written on it using a Sharpie or other similar pen. The cartridge will then be placed back in the pouch that it was removed from and the pouch will be labeled as "HVTN 119 study product or placebo 1 mL."
- The pouch containing the syringe must be labeled with a 4-hour expiration date from the time the vial is removed from the refrigerator/freezer. The label must also contain the words "Administer as soon as possible."
- One of the syringes must also be labeled for administration in RIGHT deltoid and the second syringe must be labeled for administration in the LEFT deltoid.

Any unused portion of reconstituted vials or expired prefilled syringes is disposed of in accordance with institutional or pharmacy policy.

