8.4 Administration

Any administrator of study product will be blinded to the individual participant's treatment assignment. At sites where registered pharmacists are legally authorized to administer drug, the HVTN CRS may choose to have a blinded HVTN CRS pharmacist administer the vaccinations.

Administration of vaccine or placebo for all groups consists of 2 injections, 1 each in left and right medial deltoids using the Ichor Medical Systems Intramuscular TriGrid Delivery System (TDS-IM) EP device at Months 0, 1, 3 and 6.

The TDS-IM device will be used as directed by Ichor Medical Systems, Inc. (Please refer to the TDS-IM User Manual for further instruction). The TDS-IM has three components: The TDS-IM Pulse Stimulator, the Integrated Applicator (reusable) and the Application Cartridge (single-use). The Application Cartridge is the only patient contact component of the system. Only use Becton Dickinson 3.0 mL sterile syringe (BD# 309585, 309657,

or Ichor approved) and Becton Dickinson 22 Ga x 1.5" injection needle (BD# 305156 or Ichor approved) with the Application Cartridge.

The used TDS-IM Application Cartridge should be disposed of in accordance with institutional policy in the clinic. It should NOT be returned to pharmacy.

To accommodate differences in skin thickness, a slidable depth control gauge allows adjustment of injection depth to one of three settings: 12, 17, or 22 millimeters (mm) from the skin surface. The corresponding depth of electrode insertion for these settings is 15, 20, and 25 mm respectively. Prior to applying the EP procedure, the participant's skin to muscle thickness must be assessed for each arm separately. This may be assessed once, at any time prior to the first injection with EP for a participant, and is not required prior to each procedure. However the skin fold thickness should be reassessed for a participant whose body weight has changed by 10% since the previous skin fold thickness assessment. The skin fold thickness for each arm is recorded in the participant study chart. The Application Cartridge penetration depth will be set prior to each procedure according to these measurements.

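### The pouch label prescribed for Group 2 vaccine is worded differently from the label for every Group 1 preparation, and none is given for Group 2 placebo; printed as written, the wording could reveal group.

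*Protocol*

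**What the plan says.** Protocol 8.3 tells the site pharmacist how to prepare each product and what to write on the pouch that holds the loaded cartridge. The label text is given in quotation marks each time, so it reads as exact wording.

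- 8.3.1, Group 1 vaccine at Months 0 and 1: "the pouch will be labeled as 'HVTN 119 study product or placebo 1 mL".
- 8.3.2, Group 1 placebo at Months 0 and 1, and 8.3.3, Group 1 vaccine at Months 3 and 6: "the pouch will be labeled as 'HVTN 119 study product or placebo 1mL".
- 8.3.4, Group 1 placebo at Months 3 and 6: "pouch that it was removed from and the pouch will be labeled as 'HVTN 119 study product or placebo 1 mL".
- 8.3.5, Group 2 vaccine at all four visits: "the pouch will be labeled as 'HVTN 119 or placebo 1 mL".

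The text then passes from 8.3.5 to 8.4. Protocol 8.1 defines a Group 2 placebo (Control 2, C2), but 8.3 has no preparation section and no label text for it.

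On the blind, Protocol 6.3 and SAP section 7 state that participants and site staff other than pharmacists are "blinded to both group and vaccine/control status". Protocol 8.4 adds: "Any administrator of study product will be blinded to the individual participant's treatment assignment".

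**The concern.** The blind covers group as well as vaccine status, and group is the randomised contrast of main interest. A label whose wording changes with group works against that. The person giving the injection can be expected to see the pouch: it also carries an expiry time and an instruction to administer promptly, and there are two pouches at each of four visits.

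What could be exposed is judgement by site staff. Reactogenicity severity is a primary endpoint and is compared formally (Protocol 6.4.3.1): "Kruskal-Wallis tests will be used to test for differences in severity between arms". Staff make the 25 to 60 minute assessment (Table 9-1) and all lymph node assessments (9.9.4). A participant who reports a reaction greater than mild is generally seen by a clinician within 48 hours of onset, unless it is improving or has resolved (9.9). Relationship to study product is also a staff judgement, and SAP section 5 brings it into the adverse event analyses.

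**Working it through.** **The wording.** The plan gives no figure to reproduce, so the first step is to compare the texts.

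| Protocol section | Preparation | Words *study product* on label |
|---|---|---|
| 8.3.1 | Group 1 vaccine, prime | yes |
| 8.3.2 | Group 1 placebo, prime | yes |
| 8.3.3 | Group 1 vaccine, boost | yes |
| 8.3.4 | Group 1 placebo, boost | yes |
| 8.3.5 | Group 2 vaccine | no |
| none | Group 2 placebo (C2) | not stated |

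The spacing before mL also varies, but it does not track assignment. Within Group 1 it differs between the two vaccine preparations (8.3.1 and 8.3.3) and between the two placebo preparations (8.3.2 and 8.3.4). It may come from text extraction, and nothing here rests on it.

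**What the label would tell a reader.** Inputs, from Table 3-1: 25 vaccine and 3 placebo in each group, 28 per group, 56 in all. Without the label, P(Group 1) = 28/56 = 50%, P(vaccine) = 50/56 = 89.3% and P(placebo) = 6/56 = 10.7%. Assume that labels are printed exactly as written. The C2 label must also be assumed, so both cases are shown.

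*Case A: C2 carries the short label.*
- Short label: 25 + 3 = 28 participants, all Group 2. Long label: 25 + 3 = 28, all Group 1.
- P(vaccine | short) = P(vaccine | long) = 25/28 = 89.3%, the same as without the label.
- Group is separated completely; vaccine status is not disclosed.

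*Case B: C2 carries the long label.*
- Short label: 25 of 56 = 44.6% of participants, all Group 2 active vaccine.
- Long label: 28 + 3 = 31 participants. P(Group 1 | long) = 28/31 = 90.3%, against 50% without the label.
- P(placebo | long) = (3 + 3)/31 = 6/31 = 19.4%, against 10.7%.
- Group is known with certainty for 25 participants and with 90.3% probability for the other 31. Vaccine status is known for the 25.

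The documents do not say which case applies.

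**The case against.** The strongest reply is that this is an editorial slip with no demonstrated consequence. Two words have dropped out, and the shorter label still ends with *or placebo* and names neither plasmid nor group. Protocol 6.3 states the blind explicitly and forbids pharmacy staff from discussing assignments with other site staff. The labels used in practice may be set elsewhere: section 8 refers pharmacists to the DAIDS Pharmacy Guidelines, and section 12 sends trial-specific additions to the Study Specific Procedures. Neither document is available here. Harm would need verbatim printing, the same staff seeing both wordings, those staff learning the pattern and making a rating, and that rating affecting the result. For reactogenicity, it would have to set the participant's maximum severity over all injection visits.

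Most of that stands, and it limits the point to a minor one. It does not make the text right: these are operative pharmacy instructions, and followed literally they put a wording on Group 2 vaccine pouches that no Group 1 pouch carries.

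A reader might infer more, and the documents do not support it:

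- *That the blind was broken.* Nothing shows that two label texts were printed or that any staff member linked wording to group.
- *That the label separates vaccine from placebo.* It cannot do so within Group 1. In Group 2 it depends on a C2 label that is not given; in Case A it discloses nothing about vaccine status.
- *That safety or immunogenicity comparisons are biased.* No passage says that the vaccinator also makes the reactogenicity assessment. Erythema and induration are graded mainly on measured size (11.2.2), and adverse events have no formal between-arm test (6.4.3.2). The participant marks the pain scale (9.9.3), and the breadth endpoint is a laboratory assay. No direction of bias can be argued from the text.

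**Conclusion.** The inconsistency is certain in the text: 8.3.5 prescribes a label that differs from all four Group 1 labels, and C2 has none. Because the difference runs along group, it conflicts with the intent of Protocol 6.3 and 8.4. If the labels were printed as written, and staff saw both and knew the pattern, they could infer group for all 56 participants (Case A), or for 25 with certainty and the other 31 with 90.3% probability (Case B). These figures rest on literal printing and on an assumed C2 label. Whether the Study Specific Procedures remove the difference cannot be determined here. This is a minor flaw in the protocol text that could weaken the blind; it is not evidence of unblinding or of bias.

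**What to change.** Issue a clarification memo, a route that Protocol section 13 provides for. It should correct the 8.3.5 label to the text used in 8.3.1 to 8.3.4 and state that this identical label applies to every preparation in both groups, including the Group 2 placebo. If the Study Specific Procedures already impose one label, the memo only brings the protocol into line with them.

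The cost is one short memo and a check of the label text at each pharmacy. Sample size, visits and analyses are unaffected. The absence of a C2 preparation section in 8.3 is a separate gap, which the label sentence does not close.
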